7.7 Data Analysis

The following analyses will be performed according to the availability of data from the data sources.

An overview of study analyses is included in this section. A detailed Statistical Analysis Plan (SAP) will be developed after approval of the final study protocol. For the aggregated data analyses, detailed statistical framework documents will be provided to all data owners to ensure a consistent approach.

In general, continuous variables will be summarised using descriptive statistics (mean, standard deviation, median, minimum, and maximum), while categorical variables will be summarised using frequency and percentages.

Due to the secondary use of the data, raw data will not be edited in individual listings, but aggregated data will be used according to the data source.

7.7.1 Demographic Data and Baseline Characteristics

Measures to characterize the MDS population exposed to lenalidomide and to study events of interest will include:

• Demographic data and baseline characteristics, which will be described including age, time from diagnosis to treatment, RBC transfusion burden, complete blood counts (CBCs) (white blood cells [WBC], platelets, hemoglobin levels), ferritin level, relevant medical history, co-morbidities, previous treatment of MDS and response to previous treatments, current co-medications

7.7.2 Descriptive Analyses of Lenalidomide Use Patterns in Routine Clinical Practice

The number and percent of MDS patients (both prevalent and incident) who have received at least one dose of lenalidomide will be characterized as in the labeled indication (ie, transfusion-dependent IPSS low- or int-1-risk MDS with an isolated del(5q) cytogenetic abnormality) or outside of the EU labeled indication (ie, patients with any type of MDS other than transfusion-dependent IPSS low- or int-1-risk MDS with isolated del(5q)). The rate of patients treated for MDS outside of the EU approved indication (off-label), will be provided with its 95% CI. MDS patients who are outside of the labeled EU indication will be further characterized as to the following:

- IPSS Status (Int-2 or High).
- Presence of additional cytogenetic abnormalities (yes/no) and characterization of type of additional cytogenetic abnormalities based upon the Revised International Prognostic Scoring System (IPSS-R) classification.
- Lack of documentation of transfusion-dependent status or documentation of transfusion burden insufficient to meet accepted criteria for transfusion-dependence.

It is acknowledged that patients who are out of the labeled indication may satisfy more than one of the disqualifying criteria. For the purpose of the current retrospective MDS PASS, transfusion-dependence is defined as requiring ≥ 2 RBC units over an 8-week period prior to the date of the first dose of lenalidomide treatment (due to MDS-related causes and not because of hemorrhage, trauma, or other acute cause).

In addition, patients within and outside the EU labeled indication will be characterized as to other demographic and clinical characteristics (ie, age, gender, duration of MDS, CBCs [WBC, platelets, hemoglobin levels], ferritin level, time from diagnosis to treatment, and RBC transfusion burden), relevant medical history, co-morbidities, previous MDS treatments, and current co-medications.

7.7.3 Safety Analyses

Safety analyses will be based on both the on- and off-label cohorts.

The cumulative incidence of progression to AML will be calculated and stratified according to predictive factors; 95% CIs will be calculated for each of the two cohorts. Aggregated data will be listed by country when possible.

Each registry will be requested to produce Kaplan-Meier curves for on- and off-label patients separately and to calculate the hazard ratio of on- versus off-label patients. They will also be requested to perform multivariate analyses using a Cox model including and on-/off-label indication and prognostic factors as described in the Statistical Analysis Plan on their own individual data. The respective outcomes will be provided by each registry to the study sponsor. Safety for the on- and off-label cohorts will be determined based on the incidence of reported hematological and non-hematological adverse events including SPM other than AML (which is considered as disease progression in patients with MDS). In particular episodes of neutropenia, thrombocytopenia, venous thromboembolic events, infections, bleeding, major cardiac events and SPM will be collected throughout the observational period of a patient in both cohorts as part of the clinical routine.

Due to the secondary use of the data, individual data may not be available. In these conditions, no explorative analyses on confounding or risk factors is foreseen in the protocol, except for progression to AML.

As there is no international standard to define transfusion dependence and there is a risk of error in transfusion coding, an additional sensitivity analysis will be completed to assess the impact of transfusion on the size of the on- and off-label cohorts. This sensitivity analysis will describe the proportion of off-label patients based only on IPSS categories other than low and int-1, and any karyotype other than isolated del(5q).

All safety analyses will be mainly descriptive or explorative in nature.

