The main secondary objective of the study is to assess incidence and time to progression to AML in off-label patients. Assuming a proportion of around 50%, at least 230 patients in the study will be off-label. Assuming the proportion of patients progressing to AML will be similar to those on-label, ie, 17%, 230 off-label patients will yield a 95% CI = (12.3%, 22.4%).

Incidence and time to progression to AML in on-label patients will be assessed as well for reference. Kaplan-Meier curves and hazard-ratios between on- and off-label patients will be derived and adjusted in multivariate analyses for confounding and risk factors. This will be requested to each registry, and the sponsor will provide all registries with the same statistical guidance to perform those specific analyses.

Data Analysis:

The following analyses will be performed according to the availability of data from the data sources.

For all variables

• Descriptive statistics (mean, standard deviation, median, interquartile range, minimum, and maximum) will be provided for continuous variables; categorical variables will be summarised using frequency and percentages.

Demographic data and baseline characteristics

• Demographic data and baseline characteristics will be described including age, time from diagnosis to treatment, RBC transfusion burden, complete blood counts (CBCs) (white blood cells [WBC], platelets, hemoglobin levels), ferritin level, relevant medical history, co-morbidities, previous treatment of MDS and response to previous treatments, current co-medications, morphology and cytogenetic results (MDS subtype, blast count, karyotype), and data on risk classifications (IPSS).

Study drug exposure

The primary objective of the study is to describe the pattern of use of lenalidomide in the clinical routine practice of MDS patients. The proportion of patients receiving lenalidomide outside of the EU approved indication will be provided and will be associated with its 2-sided 95% CI. For lenalidomide, indication for which lenalidomide is used and dosing including any adjustments will be summarised using descriptive statistics. Duration of dosing will be similarly summarised together with a summary of dosing interruptions. Duration of exposure and cumulative dose of lenalidomide will also be described. Data on the use of relevant concomitant medication will also be reported.

Safety analysis

Safety analyses will be based on both the on- and off-label cohorts.

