Lenalidomide and Risk of AML Progression in Patients with Transfusion-dependent IPSS Low- or Int-1–Risk MDS Del(5q)

A retrospective analysis was published (Kuendgen, 2012a) comparing the risk of progression to AML and OS in patients treated with lenalidomide (from Studies MDS-003 and MDS-004 combined (Fenaux, 2011; List, 2006) with that of similar patients from the Düsseldorf MDS Registry (previously described) who never received lenalidomide (Germing, 2012). The comparative study included only patients with transfusion-dependent anemia without concomitant thrombocytopenia (< $50,000/\mu$ L) or neutropenia (< $500/\mu$ L) to have comparable populations. Overall, the 2 cohorts included 295 lenalidomide-treated and 125 untreated patients.

To account for differences in person-time at risk in these 2 cohorts due to different starting points for follow-up (from diagnosis in the untreated cohort versus inclusion in the study for the treated cohort), *left truncation* was considered appropriate and adopted for all analyses in this study. The 2 cohorts were well balanced, except for a higher transfusion need for treated versus untreated patients (median of 6 versus 2 units of RBC/8 weeks); higher transfusion dependence is a well-known risk factor for progression to AML and reduced survival (Malcovati, 2006).

Based upon the competing-risk estimator with left truncation, the 2-year cumulative incidence of progression to AML was 6.9% and 12.1% for the cohort of treated versus untreated patients, respectively; the respective 5-year cumulative incidence was 22.8% and 19.9% (Kuendgen, 2012a). Two-year survival was 89.9% versus 74.4% in treated versus untreated patients. After adjustment for covariates, the risk of progression to AML was similar in the 2 cohorts (hazard ratio [HR] = 0.969), while the risk of death was significantly reduced in the lenalidomide-treated cohort (HR = 0.597, p = 0.012). The authors concluded that the treatment of patients with low- or int-1–risk MDS and del(5q) with lenalidomide did not increase the risk of progression to AML, but it possibly conferred a survival benefit in RBC transfusion-dependent patients with del(5q) low- or int-1–risk MDS.

A similar study previously compared the time to AML progression and survival in 95 low- or int-1–risk MDS del(5q) patients treated within the French ATU (Authorisation Temporaire d'Utilisation) cohort to 99 similar patients of the GFM (French MDS Group) who never received

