An interim descriptive report was prepared 1 year after study start. Within the interim descriptive report, available data on eligible patients regarding the pattern of use of lenalidomide within and outside the EU approved indication, namely the distribution of MDS patients according to predefined categories (eg, transfusion-dependent IPSS low- or int-1-risk MDS with isolated del(5q), or with additional cytogenetic abnormalities, or IPSS risk categories int-2 or high, or patients with MDS without del(5q)) was presented. On 29-Mar-2019, the first interim descriptive report was submitted to the Pharmacovigilance Risk Assessment Committee (PRAC) in order to discuss if the data collected on lenalidomide use, across different groups of MDS patients, are sufficient to allow successful completion of this study. The Assessment Report adopted by the CHMP on 27-Jun-2019 included a request to submit another interim descriptive report in Quarter (Q)1 2020. On 27-Mar-2020, the second interim descriptive report was submitted to PRAC (EMEA/H/C/000717/ANX/041.8). The final Assessment Report, adopted by the CHMP on 10-Dec-2020, concluded that the post-authorisation measure for the second interim report was fulfilled with no further action required.

The final data analysis will occur after at least 460 patients have been included and will be based on data from all eligible patients available at that time.

Data will be collected for both on- and off-label patients, to cover the period from date of first lenalidomide dose (baseline) until the date of death or last follow-up available at the time of the retrospective data collection (whichever occurs first) including for patients lost to follow-up or who discontinue the drug for any reason. Data collected at baseline will include those data that could have been generated earlier but are relevant at the baseline date (for example, information related to diagnosis).

Time to progression to AML or time to any other kind of event will be counted from the date of first lenalidomide dose (baseline).

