CHF = congestive heart failure; EPO = erythropoietin; EU = European Union; IPSS = International Prognostic Scoring System; IPSS-R = revised IPSS; MDS = myelodysplastic syndromes; MI = myocardial infarction; NMSC = non-melanoma skin cancer; PD = progression of disease; VTE = venous thromboembolic event; WHO = World Health Organization,

^a As far as available in data sources and as per clinical practice

^b Cytogenetic risks will be categorized as described in the new cytogenetic scoring system (Schanz, 2012) that has been integrated into the IPSS-R (Greenberg, 2012).

Table 4: Therapy and Other Treatment Variables for Both On- and Off-label Cohorts

Variables ^a	
Lenalidomide Treatment	Indication of use, starting dose, dose adjustments, dose interruptions
Other MDS medications	Current use (yes, no); dose, response, duration of use
Prior ESA Treatment	Prior use (yes, no); prior response (yes/no), most recent treatment, duration of treatment
Other Prior MDS Treatments	Prior use (yes, no); prior response (yes/no), most recent treatment, duration of treatment
Concurrent ESA Use	Current use (yes, no); dose, response, duration of use
Concomitant Medications	Concomitant medications, duration of treatment
RBC transfusion	Yes/no, number of units over last 8 weeks (baseline and until PD)
Con = concomitant ESA	= erythropoiesis-stimulating agent. MDS = myelodysplastic syndromes

Con = concomitant; ESA = erythropoiesis-stimulating agent; MDS = myelodysplastic syndromes; Meds = medications; PD = progression of disease; RBC = red blood cell.

^a As far as available in data sources and as per clinical practice

Variables ^a	
Progression to AML ^b	Yes/no, date of event, and method of documentation
Death	Date and cause of death, and method of documentation
Adverse Events	Date of event (incidence) (using case definitions from NCI CTCAE where feasible) of hematologic and non-hematologic adverse events, including but not limited to neutropenia, thrombocytopenia, VTEs, infections, bleeding, and major cardiac events
SPM (Invasive [hematologic and solid tumors] and NMSC) ^c	Yes/no, date of event, and method of documentation

Table 5: Outcome Variables for Safety for Both On- and Off-label Cohorts

AML = acute myeloid leukemia; CTCAE = Common Terminology Criteria for Adverse Events; NCI = National Cancer Institute; NMSC = non-melanoma skin cancer; SPM = second primary malignancy; VTE = venous thromboembolic event.

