This retrospective drug-utilisation study will include patients with MDS treated with lenalidomide, irrespective if within or outside the approved indication in the EU (eg, patients commencing lenalidomide treatment for transfusion-dependent IPSS low- or int-1-risk MDS with isolated del(5q), or with additional cytogenetic abnormalities, or IPSS risk categories int-2 or high, or patients with MDS without del(5q) will also be recorded).

The primary objective of the study is to evaluate the proportion of patients outside of the EU approved indication (off-label). Feasibility assessments indicated that off-label use of lenalidomide in MDS in the EU is infrequent (5% to 22% with a large margin of error at either end). However, the second interim descriptive report submitted to PRAC on 27-Mar-2020 (EMEA/H/C/000717/ANX/041.8) showed a higher level of off-label use. The proportion of MDS patients treated in an off-label setting was high, with 57.0% of MDS patients treated off-label (n = 212) versus 40.1% of MDS patients treated on-label (n = 149), and 2.9% of patients with an unknown label status (n = 11). Assuming that the final percentage of off-label patients will be around 50%, a sample size of 460 patients will yield a 95% CI = (45.4%, 54.6). The sample size calculated would not only allow to investigate this assumption, but also will detect smaller percentages if the true proportion would be smaller.

Assuming a proportion of around 50%, around 230 patients in the study will be off-label. Assuming the proportion of patients progressing to AML will be similar to those on-label, ie, 17%, 230 off-label patients will yield a 95% CI = (12.3%, 22.4%).

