7.6 Data Management

Study Monitoring and Source Data Verification

The data is in this study will be owned by the data owners including, but not limited to, the data sources described in Section 7.4. All individual data management, data security, and data protection requirements will be the responsibility of the data owners (ie, registries). For all results provided to Celgene, security of the results will be maintained at all times in line with applicable local law and procedures. Access to results will be limited to authorised individuals. Controls, such as document encryption, will be used to ensure the authenticity, integrity, and confidentiality of electronic records when transmitted over open systems (eg, the internet). Adequate back up of the data will be maintained throughout the course of the study.

The management of missing data as potential sources of study biases will be done when analyzing the distribution of available data on eligible patients and the outcomes from longitudinal follow-up, as described in Section 7.9 "Limitations of the Research Method".

The data required for classifying patients as on- or off-label are critical to satisfy the primary objective of this study. An attempt will be made to obtain values when data are missing. However, if data cannot be found to classify lenalidomide patient as on- or off-label, that patient cannot be classified and will be dropped from the primary analysis.

For the analyses of time to progression to AML (Kaplan-Meier and multivariate analyses adjusted for confounding and risk factors) to be performed at the end of study, data owners will be provided with instructions and will be requested to perform this analysis on an individual registry basis. This approach will ensure that all data have appropriate legal and data protection requirements fulfilled. All such data will be pseudonymized by the registries and processed in accordance with local regulations regarding privacy protection.

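### Kaplan-Meier is the only estimator named for time to AML; with deaths without AML in effect censored, its complement overstates the absolute AML risk

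*Protocol*

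**What the plan says.** The Abstract (Study Size) sets the weight of this endpoint: "The main secondary objective of the study is to assess incidence and time to progression to AML in off-label patients".

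The analysis is described in two places.

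- Section 7.7.3: "Each registry will be requested to produce Kaplan-Meier curves for on- and off-label patients separately". Each registry also calculates an on- versus off-label hazard ratio and fits a Cox model.
- Section 7.6 makes clear that the curves concern AML itself, not a composite with death: "For the analyses of time to progression to AML (Kaplan-Meier and multivariate analyses adjusted for confounding and risk factors").

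Just before the Kaplan-Meier sentence, Section 7.7.3 plans a second summary: "The cumulative incidence of progression to AML will be calculated and stratified according to predictive factors", with 95% CIs for each cohort. It does not say how this is estimated.

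Section 7.1.1 has data run from the first dose "until the date of death or last follow-up available at the time of the retrospective data collection (whichever occurs first"). Table 5 in Section 7.3 lists "Date and cause of death, and method of documentation" as a variable. Neither the analysis sections nor the limitations in Section 7.9 treat death without AML as a competing event. A competing-risk method appears only in Section 5.2, for one cited comparison of treated and untreated patients: "Based upon the competing-risk estimator with left truncation, the 2-year cumulative incidence of progression to AML was 6.9% and 12.1" per cent respectively.

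**The concern.** A patient who dies without AML can no longer progress. Kaplan-Meier applied to time to AML handles that patient like one lost to follow-up, who might still progress later. The complement of the curve therefore estimates AML risk in a hypothetical setting without other deaths. It is never lower than the real cumulative incidence, and it is higher wherever deaths without AML precede later AML events.

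Death is common in this disease. Section 5.2 quotes median survival of 35.5 to 44.4 months across the phase 3 trial arms, and survival as low as 7 months in patients with additional risk factors.

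At stake is the absolute AML risk in each cohort, a central description for a safety study of this kind. The estimator also matters early. The registries run these analyses on common instructions from the sponsor, and Section 7.9 says raw data cannot be pooled, so a poor choice is hard to repair centrally afterwards.

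**Working it through.** **1. The plan's own figure.** Section 7.5 assumes 17% progression and states that "230 off-label patients will yield a 95% CI = (12.3%, 22.4" per cent). Taking 39 of 230 (17.0%), the Clopper-Pearson interval is 12.3% to 22.4%, which reproduces it. The margins are 17 − 12.3 = 4.7 points below and 22.4 − 17 = 5.4 points above. This is a binomial calculation and is not affected by the point made here.

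**2. Formulas.** Let *a* be the hazard of AML and *d* the hazard of death without AML, both constant over time *t* (assumption).

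- What the Kaplan-Meier complement estimates: 1-KM = 1 − exp(−*at*)
- Real cumulative incidence: CIF = *a*/(*a*+*d*) × [1 − exp(−(*a*+*d*)*t*)]
- Net risk of death without AML: *m* = 1 − exp(−*dt*)

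**3. Excess at a true incidence of 17%.** The documents give no *m*, so a range is shown. For each *m*, *a* is solved so that CIF = 17%. The result depends only on *at* and *dt*, so it is the same for a 2-year and a 5-year horizon.

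| Net risk of death without AML | 1-KM | Excess (points) |
|---|---|---|
| 10% | 17.9% | 0.9 |
| 20% | 18.9% | 1.9 |
| 30% | 20.1% | 3.1 |
| 40% | 21.5% | 4.5 |
| 50% | 23.2% | 6.2 |
| 60% | 25.4% | 8.4 |

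Check of the 30% row: *dt* = −ln(0.70) = 0.357 and *at* = 0.224. CIF = 0.224/0.581 × (1 − exp(−0.581)) = 0.386 × 0.441 = 0.170. 1-KM = 1 − exp(−0.224) = 0.201.

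The excess passes the upper planning margin of 5.4 points between the 40% and 50% rows.

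**4. Equal AML hazards, different mortality.** Fix *a* so that 5-year 1-KM is 17.0%: *a* = −ln(0.83)/5 = 0.0373 per year. Set *d* = ln 2 ÷ (median time to death without AML, in years).

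| Assumed median | 5-year 1-KM | 5-year CIF | Ratio |
|---|---|---|---|
| 44.4 months | 17.0% | 11.2% | 1.52 |
| 35.5 months | 17.0% | 10.2% | 1.67 |
| 24 months | 17.0% | 8.3% | 2.05 |
| 12 months | 17.0% | 5.0% | 3.42 |

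The first two medians are borrowed from the phase 3 arms. They are all-cause (ln 2/3.70 = 0.19 and ln 2/2.96 = 0.23 per year) and include deaths after AML, so they overstate *d* for those arms. The last two are illustrative.

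**5. Unequal AML hazards.** Over 5 years, *a* = 0.08 and *d* = 0.10 give 33.0% against 26.4%, an excess of 6.6 points (ratio 1.25). With *a* = 0.02 and *d* = 0.20 the figures are 9.5% against 6.1%, an excess of 3.5 points before rounding (ratio 1.57). Mortality is higher in the second case, yet the excess in points is smaller.

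**The case against.** The strongest reply is that Section 7.7.3 already plans a cumulative incidence of AML with 95% CIs by cohort, and Section 7.7 leaves detail to an SAP that is not shown. That summary could be a competing-risk estimate, and the protocol nowhere says that 1-KM will be reported as AML risk. This limits the point but does not remove it. The protocol itself fixes Kaplan-Meier for time to AML, and in the Kaplan-Meier and Cox paragraph it refers to the SAP only for the prognostic factors. No section provides for death without AML as a competing event.

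It is also fair that the safety analyses are described as mainly descriptive or explorative. Interpretation is at stake, not a test.

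A reader might infer more than the documents support:

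- *That the off-label cohort, or the cohort with higher mortality, is necessarily more affected.* No mortality by cohort is given, and step 5 shows that the excess in points depends on the AML hazard too.
- *That the on/off-label hazard ratio is biased.* With deaths censored, the Cox model estimates a valid cause-specific hazard ratio. It only needs that label.
- *That all the reference figures in Section 5.2 are competing-risk estimates.* This is stated for one cited study. Another is described as using left truncation, with no competing-risk estimator named, and the 16.8% two-year risk from the phase 3 trial has no named estimator.
- *That patients enter a registry after their first dose and need delayed-entry handling.* The protocol does not say so. Its prevalent patients are those diagnosed before EU approval who start lenalidomide on or after it.

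**Conclusion.** The point holds for absolute AML risk. As written, the only named time-to-AML estimator in effect censors deaths without AML, and 1-KM read as risk would be too high. At a true 17% the excess is about 1 to 8 points for a net risk of death without AML of 10% to 60%. At the upper end this exceeds the margin of about 5 points in the plan's own interval; at the lower end it is minor. These sizes rest on constant hazards and on an assumed mortality range, because the protocol gives no rate of death without AML.

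For equal AML hazards the overstatement rises with mortality; its direction between the two cohorts cannot be determined from the documents. The primary objective, the study size and the cause-specific hazard ratio are not affected.

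**What to change.** In Sections 7.6 and 7.7.3, the matching Abstract text and the registry instructions:

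1. Name Aalen-Johansen as the estimator for the cumulative incidence of AML by cohort, with death without AML as the competing event. Report 2- and 5-year estimates with 95% CIs.
2. Label the Cox hazard ratio as cause-specific. Report deaths without AML by cohort, or fit the matching cause-specific model for that event.
3. Keep Kaplan-Meier, if wanted, for AML-free or overall survival, and state that 1-KM is not to be read as AML risk.

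Delayed entry should be added only if registry enrolment is shown to follow the first dose.

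The cost is wording and one shared program for the registries. Date and cause of death are already planned variables, so no new data item is needed. The change should be made before the registries run their analyses.
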